8.2 Tissue Immunohistochemistry Studies

8.2.1 Tissue Procurement

Tumor samples will be requested from all patients. A formalin fixed paraffin embedded tumor tissue sample (or newly obtained formalin fixed biopsy of a tumor lesion not previously irradiated) will be procured in the form of at least five unstained slides. Cytologic specimens will not be acceptable. If additional biopsies are performed during scheduled cystoscopies throughout the study, an additional 5 unstained slides from each will also be obtained for IHC studies only if the sample contains tumor tissue. See separate lab manual for details on processing and shipping.

8.2.2 Assay Methodology

Briefly, paraffin-embedded tumor specimens will be deparaffinized in xylene and rehydrated in a graded series of alcohols. Slides will be unmasked in Target Retrieval Solution (DakoCytomation, Glostrup, Denmark) using a Decloaking Chamber (Biocare Medical, Walnut Creek, Calif) and then blocked for endogenous peroxidase for 5 minutes with a peroxidase blocking solution. Slides will be rinsed in TRIS-buffered saline with 0.1% Tween-20 (TBST), incubated for 30 minutes with 1.5% normal horse serum in TBST, rinsed in TBST, and blocked for endogenous avidin and biotin. Slides will then be incubated overnight at 48C with an anti-PD1, anti-PD-L1 and anti-PD-L2 antibodies (BD Biosciences). Tissue slides will be incubated with respective antibodies at a concentration of 1:100. This step will be followed by 30 minutes of incubation with biotinylated horse antimouse IgG and avidin/biotin complex reagent. Slides will be amplified using a Tyramide Signal Amplification Biotin System (Perkin-Elmer, Boston, Mass) and incubated in 3-amino-9-ethylcarbazole chromogen. Isotype-matched antibodies were used to control for nonspecific staining.

Hematoxylin/eosin and PD-1, PD-L1 and PD-L2-stained sections will be reviewed by a urologic pathologist. Criteria to be evaluated include: World Health Organization/International Society of Urologic Pathology (WHO/ISUP) histologic subtype and grade, TNM 2002 pathologic tumor stage, the presence and type of intratumoral lymphocytic infiltration, and the quantity and location of PD-L1 staining. The tumor will be considered positive for PD-1, PD-L1, PD-L2 if >5% of tumor cells had histologic evidence of plasma membrane staining.

8.3 NGS

Ten FFPE unstained slides, 5 μ m sections on positively charged, unbaked slides and a terminal H&E slide and matched normal sample (blood) will be stored in the [name] Lab until analysis. Analysis will be performed on archived tissue samples obtained at baseline and on fresh tissue from any subsequent biopsies performed during cystoscopies scheduled for weeks 17, 25, 33, 41, 49 and at progression.

8.4 Urinary cytokines and lymphocyte phenotypes

Urine samples will be collected in a sterile plastic cup from each patient 30 min before and an optional sample at the third void approximately 4-6 hours after BCG and/or pembrolizumab administration throughout treatment (weeks -2, 0, 1, 2, 3, 4, 5, 7, 9, 11, 13, 15, 17, 21, 25, 29, 33, 37, 41, 45, and 49). NOTE: The first void will be 2 hours post-dosing as part of the treatment and the second void after dosing will not be used for any correlative studies and should be discarded. An optional urine for research will be

NU Study Number: NU 15U06
Merck Study Number: 3475-265

obtained at the third void, which is typically 4-6 hours after dosing; however the time does not need to be exact and may be adjusted depending on patient needs/urgency.

Samples will be transported to the Pathology Core Facility for processing. See separate lab manual for processing details.

8.5 Peripheral blood cytokine assays and lymphocyte phenotypes

Two 3 mL lavender EDTA tubes will be collected from patients prior to dosing at weeks -2, 0, and 17 at the time of other lab collection. One tube of blood will be transported immediately to the Flow Cytometry Core Laboratory for processing. Lymphocyte subsets (CD3, CD4, CD8, CD11c, CD19, and CD 45, CD56, Gr-1) will be analyzed according to absolute cell numbers per microliter of whole blood, percent representation among all lymphocytes, and coexpression of the activation markers CD25, HLA-DR, and CD45RO using automated flow cytometric techniques at the Flow Cytometry Core Laboratory, Robert H Lurie Cancer Center of Northwestern University under the supervision of [name].

The second tube of blood will be processed in the Pathology Core Facility prior to shipment to Myriad Laboratories for cytokine analysis. A portion of the blood specimens that have been collected for cytokine analysis (time-points week -2, week 0, and week 17) may be used in plasma PK assays, per Principal Investigator discretion.

8.6 Specimen Banking

Patient samples collected for this study and not entirely exhausted by the studies described above will be retained in the [name] Lab (see separate lab manual for location details). Specimens will be stored indefinitely and may be used for future, unspecified testing. If future use is denied or withdrawn by the patient, best efforts will be made to stop any additional studies and to destroy the specimens.

[name], PhD will be responsible for reviewing and approving requests for clinical specimen from potential research collaborators outside of Northwestern University. Collaborators will be required to complete an agreement (a Material Transfer Agreement or recharge agreement) that states specimens will only be released for use in disclosed research. Any data obtained from the use of clinical specimen will be the property of Northwestern University for publication and any licensing agreement will be strictly adhered to.

The following information obtained from the subject's medical record may be provided to research collaborators when specimens are made available:

- Diagnosis
- Collection time in relation to study treatment
- Clinical outcome – if available
- Demographic data

9 STATISTICAL CONSIDERATIONS

This is a Phase I dose escalation study using the 3+3 design with 4 doses. The dose escalation scheme and rules for determining the primary outcome, the maximum tolerated dose, are described in Section 4.3. In order to achieve up to 24 evaluable patients for dose limiting toxicity and MTD determination, up to 27 patients may be accrued to the study. This 3+3 design has a 91% chance (49%, 17%) of dose escalating when the true toxicity rate for that dose is 10% (30%, 50%).

To achieve the secondary objectives, the dose limiting toxicities and adverse events will be presented as descriptive frequencies and proportions. Serious adverse events will be summarized by type, frequency, timing, severity and attribution.

NU Study Number: NU 15U06
Merck Study Number: 3475-265

Exploratory objectives (PK, response, progression, immune markers) will be summarized with descriptive statistics due to the anticipated small study sample size. Progression free survival (PFS) and overall survival (OS) will be analyzed using the Kaplan-Meier method. The median PFS and OS estimates will be reported along with confidence intervals.

Progression free survival (PFS) time is calculated as the time that elapses between the initiation of trial therapy and the day of first documented disease progression or death from any cause (whichever is sooner) for all eligible subjects who receive at least one dose of trial therapy. If subsequent anti-cancer therapy is initiated without a preceding disease progression, PFS will be censored at the time of initiation of the subsequent anti-cancer therapy. If disease progression or death from any cause is not observed prior to completion of study participation or initiation of subsequent anti-cancer therapy, the PFS will be censored as the last available disease assessment.

Overall survival (OS) time is calculated as the time that elapses between the initiation of trial therapy and the date of death from any cause, date of completion of study participation, or date the subject is lost to follow up (whichever is sooner) for all eligible subjects who receive at least one dose of trial therapy. If death from any cause is not observed prior to completing study participation, the OS will be censored as the time of the last available documentation of survival status.

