2.3 Exploratory Objectives & Endpoints

2.3.1 To characterize the pharmacokinetics (PK) of pembrolizumab in both blood and urine when administered intravesically in combination with BCG. This will be done on the first 3 patients only to provide exploratory data. (A limited amount of plasma PK testing may be performed on additional patients as described below.*) PK will be evaluated by serial blood and urine sampling at specified time points before and after treatment (described in Section 5) during weeks -2 and 4 for determination of plasma and urine concentration-time profiles and PK parameters of pembrolizumab. Blood PKs will be performed by an outside vendor; urine will be collected and stored in the [name] Lab for later analysis.

*A portion of the blood specimens that have been collected for cytokine analysis (time-points week -2, week 0, and week 17) may be used in plasma PK assays, per Principal Investigator discretion.

2.3.2 To measure humoral and cellular responses to tumor antigens on serum and urine samples by measuring the levels of cytokines (i.e., IL-2, IL-6, IL-8, IL-10, IL-18, IFN γ and TNF- α) and peripheral blood lymphocyte phenotype throughout treatment. Urine and blood samples will be collected before and

after dosing throughout treatment (as described in the study schema). Cytokines will be measured using ELISA assays. Lymphocyte profiles will be analyzed using automated flow cytometric techniques.

- 2.3.3 To determine the response rate in terms of complete pathologic response in this population assessed when patient undergoes cystoscopies (weeks 17, 25, 33, 41, and 49 if applicable). Patients will be examined via bladder cystoscopy and may undergo biopsy for pathological confirmation if needed. Responses will be categorized as yes or no for bladder recurrence.
- 2.3.4 To document the progression rate associated with the combination of intravesical pembrolizumab and BCG in patients with high risk or BCG-refractory non-muscle-invasive bladder cancer. Tumor progression will be defined as positive transurethral resection and/or biopsy.

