3 PATIENT ELIGIBILITY

The target population for this study is patients with high risk or BCG-refractory non-muscle invasive bladder cancer. This will be a single-center trial conducted in the Northwestern

NU Study Number: NU 15U06
Merck Study Number: 3475-265

Medicine Developmental Therapeutics Institute in conjunction with the Department of Urology of Northwestern University at Northwestern Medicine.

Up to 24 evaluable subjects will be needed for this trial, therefore up to a total of 27 may be enrolled in order to achieve the necessary number of evaluable subjects. BCG-refractory is defined as tumor recurrence within 6 months of receiving at least 2 courses of intravesical BCG (at least 5 or 6 inductions and at least 2 or 3 maintenance doses) or T1 high grade disease at the first evaluation following induction BCG alone (at least 5 or 6 induction doses). Therefore, patients who develop a recurrence of bladder cancer during maintenance treatment period with BCG will be also eligible to the present study. However, patients who were not able to complete prior induction BCG treatment because of intolerable toxicities and developed a recurrence will not be eligible for this trial given increased risk of adverse events with repeated exposure.

On average, 1-2 high risk or BCG-refractory potentially eligible patients are seen per month in the Urology clinic, and it is anticipated that one patient will be accrued every 2-3 months. Potential patients may be referred to the Principal Investigator (PI) at Northwestern University, [name], at [contact]. In addition, the sub-investigators have significant experience and collaborations with nearby university and community urology groups to help provide additional referrals for this high priority study when activated.

Eligibility will be evaluated by the study team according to the following criteria. Eligibility waivers are not permitted. Subjects must meet all of the inclusion and none of the exclusion criteria to be registered to the study. Study treatment may not begin until a subject is registered. Please refer to Section 10.3 for complete instructions regarding registration procedures.

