4.9.2 Follow-Up Visits

After discontinuing trial therapy, patients will be followed clinically for disease recurrence and survival according to the below schedule. There is no specific limit on the length of follow-up, as it is intended to follow all patients for survival.

After the last dose of trial therapy, follow patients:

- Every 3 months (\pm 30 days) during years 1 and 2;
- Every 4 months (\pm 60 days) during years 3 and 4;
- Every 6 months (\pm 60 days) during years 5 and 6;
- Every 12 months (\pm 90 days) thereafter;
- Or until death, withdrawal, or end of study (whichever occurs first).

Information regarding post-study anti-neoplastic treatment will be collected if new treatment is initiated.

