10.7 Publication Policy

All potential publications and/or data for potential publications (e.g. manuscripts, abstracts, posters, clinicaltrials.gov releases) must be approved in accordance with the DSMC Data Release Policies and Processes. The assigned QAM will prepare a preliminary data set for DSMC approval no later than 3 months after the study reaches its primary completion date, as defined by ClinicalTrials.gov. This is the date that the final patient was examined or received an intervention for the purposes of final collection of data for the primary outcome, whether the clinical trial concluded according to the pre-specified protocol or was terminated. If the investigator would like data release to be approved by the DSMC prior to when study design specifies, and/or prior to three months after a study's primary completion date, the PI must send a written request for data approval to the QAM which includes justification. Requests must be made a minimum of six to eight weeks in advance of the expected deadline. The request will be presented to the DSMC at their next available meeting. Any DSMC decisions regarding data release will be provided to the PI. If the request is approved, the QAM will present the data set to the DSMC for approval. A final, DSMC-approved dataset, as applicable, will then be released 6-8 weeks after the request was made. The investigators are expected to use only DSMC-approved data and statistical analyses any time they are disseminating trial data. The investigators must send a copy of the draft abstract/poster/manuscript to the study's biostatistician and assigned QAM to confirm that the DSMC-approved data and statistical analyses are used appropriately. Once the biostatistician and QAM gives final approval, the publication may be submitted to external publisher.

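### The progression rate in objective 2.3.4 has no time point, so with staggered cohorts and open-ended follow-up its value depends on the data cut-off

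*Combined protocol and SAP*

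**What the plan says.** Objective 2.3.4 reads "To document the progression rate associated with the combination of intravesical pembrolizumab and BCG", and the event is given without a horizon: "Tumor progression will be defined as positive transurethral resection and/or biopsy". PFS is a separate objective (2.3.8).

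Section 9 treats the two differently. Progression falls under "Exploratory objectives (PK, response, progression, immune markers) will be summarized with descriptive statistics due to the anticipated small study sample size". The next sentence gives the time-to-event method for the other endpoints: "Progression free survival (PFS) and overall survival (OS) will be analyzed using the Kaplan-Meier method". Medians with confidence intervals are promised for PFS and OS. No time point, denominator or data cut-off is given for the progression rate.

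Three other places fix how unequal follow-up will be:

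- Section 3, on accrual: "it is anticipated that one patient will be accrued every 2-3 months".
- Section 4.3: dose levels are filled in order, 3 to 6 patients each. Escalation waits until a group of three has completed the DLT period of 2 + 7 = 9 weeks.
- Section 4.9.2: "There is no specific limit on the length of follow-up, as it is intended to follow all patients for survival".

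**The concern.** A rate needs a period. If 2.3.4 is reported as progressors over patients treated, someone observed for five months and someone observed for five years count equally, and the first is scored as a non-progressor simply for lack of time. The reported figure then reflects the date of the data cut as well as the regimen. Two analysts working from the same plan at different dates could report quite different rates.

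Dose level is tied to calendar time in this design, so a breakdown by level would carry the same artefact: later, higher doses would have shorter follow-up and fewer observed progressions even if dose made no difference. That matters to anyone using the result to plan a later efficacy trial. It does not touch the DLT-based primary outcome.

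**Working it through.** **The plan's own figures.** The documents give no number for progression. Their one computed design figure, the escalation probability (1−p)³ + 3p(1−p)²·(1−p)³, gives 90.6%, 49.4% and 17.2% at p = 10%, 30% and 50%. This matches the stated 91%, 49% and 17% and has no bearing on this point.

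**Spread of start dates, from the protocol's own inputs.** Months are weeks / 4.345.

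- Fastest case (2 months per patient, 3 per level): each group of three takes 2 + 2 + 9/4.345 = 6.07 months, so level 4 starts on average 3 × 6.07 = 18 months after level 1.
- Slowest case (3 months per patient, 6 per level): 18 × 3 = 54 months.

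**Assumptions not in the documents.** 40% progression at 12 months, the same constant hazard at every level, one patient per 2.5 months (the midpoint of the stated range, longer than the 9-week pause), levels filled in order, no losses, and an illustrative cut-off 22 weeks (5.06 months) after the last first dose.

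- Hazard: h = −ln(1 − 0.40)/12 = 0.0426 per month.
- Follow-up of patient i of N: f = 5.06 + 2.5(N − i). The longest is 5.06 + 27.5 = 32.6 months for N = 12, and 5.06 + 57.5 = 62.6 months for N = 24.
- Expected crude rate: the mean of 1 − exp(−h·f).
- Example, level 4 with three patients: f = 10.06, 7.56 and 5.06 give 35%, 28% and 19%, mean 27%.

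For the variant in which half never progress, the hazard among the rest is −ln(1 − 0.40/0.50)/12 = 0.134 per month, and the result is multiplied by 0.5.

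| Case | Level 1 | Level 2 | Level 3 | Level 4 |
|---|---|---|---|---|
| 3 per level | 72% | 62% | 47% | 27% |
| 6 per level | 91% | 82% | 67% | 37% |
| 6 per level, half never progress | 50% | 50% | 48% | 37% |

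With 6 per level, a 12-month rate of 30% gives 81/70/54/28%, and 60% gives 99/96/86/56%.

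**Moving the cut-off, all levels pooled.** The same formula, with 5.06 replaced by 12, 24 or 36 months:

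| Case | 22 weeks | 12 months | 24 months | 36 months |
|---|---|---|---|---|
| 3 per level | 52% | 64% | 79% | 87% |
| 6 per level | 69% | 77% | 86% | 92% |

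The 12-month risk is 40% throughout. If half never progress (6 per level), the pooled rate moves only from 46% to 50%.

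**A second set of assumptions.** With a 24-month median and both accrual extremes, levels 1 and 4 show 52% vs 18% (fastest) to 85% vs 30% (slowest) at nine weeks plus three months after the last first dose. When the last patient reaches week 49 they show 60% vs 33% to 88% vs 42%. A further 24 months on, they show 80% vs 66% to 94% vs 71%. The gap narrows but does not close quickly.

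**Fixed horizon.** Week 49 is 51 weeks (11.74 months) after the week −2 dose. Under the 40% assumption the expected rate is 1 − exp(−0.0426 × 11.74) = 39% at every level, whatever the cut-off, once follow-up extends that far.

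**The case against.** Several things count against a strong version of this point, and most of them stand.

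- **The method is inferred.** Section 9 says descriptive statistics; it uses the word proportions only for DLTs and adverse events. A crude proportion is the natural reading of a progression rate, but it is not the text. The missing time point remains either way.
- **Kaplan-Meier PFS is already planned.** It runs from each patient's own first treatment, has censoring rules, and covers progression or death, so a sound analysis of nearly the same event will sit beside the rate. But PFS is a different endpoint, and only its median is named for reporting.
- **No efficacy table by dose is planned.** A reader might infer that the plan will show higher doses doing better. The documents do not support that: 2.3.4 concerns the combination as a whole. Re-opening a lower level to reach six patients (Section 4.3) would also partly break the link between dose and time.
- **The size rests on assumptions.** The documents give no progression hazard for this regimen. Six at every level, filled in order, needs exactly one DLT in the first three and none in the next three at each of levels 1 to 3. That probability, 3p(1−p)²(1−p)³, is at most 0.20 per level, so about 0.20³ = 0.8% for all three. The three-per-level case is the better guide.
- **A window could be read in.** Study cystoscopies end at week 49. If only progression up to then is counted, the early cut-off gives 39/39/39/27% with three per level. But 2.3.4 states no such window.
- **Section 10.7 does not set the cut.** It calls for "a preliminary data set for DSMC approval no later than 3 months after the study reaches its primary completion date", and one might infer that progression will be analysed that early. The section assigns neither progression nor the adverse-event summary to that data set and allows other releases, so the 22-week cut-off above is only an illustration. Nothing here shows a bias in the adverse-event tables.

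**Conclusion.** The concern holds in a limited form. The progression rate is a separate reported objective with no time point, in a design where mean start dates differ by about 1.5 to 4.5 years between the lowest and highest level and follow-up is open-ended. Read in the natural way, it depends on the cut-off date. The movement could be large (52% to 87% overall with three per level) or slight (46% to 50% with six per level if half never progress), depending on an unknown hazard. The pattern by dose arises only if such a table is made, and it narrows with longer follow-up. The direction of the cut-off effect does not depend on the assumed rate; its size does. Severity is minor: the objective is exploratory, and neither the MTD nor escalation is affected.

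**What to change.** In Section 9, take progression out of the descriptive-statistics sentence and add text to this effect:

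- Objective 2.3.4 is reported as the cumulative incidence of progression, with death before progression as a competing event (or as a Kaplan-Meier estimate), at a fixed time from first dose. The existing week 49 cystoscopy is a suitable choice.
- The number at risk at that time is given, and the estimate is taken once the last treated patient has reached that visit or left treatment.
- Kaplan-Meier PFS is reported at the same time point, beside its median.
- If results are shown by dose level, follow-up per level is shown with them.

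The cost is two or three sentences and a data cut at that point. No new assessments are needed. The one downside is that this exploratory figure is reported later than the MTD.
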